### ***9.2 Missing Data***

Missing data arising from teeth where the Calcivis System assessment is uninterpretable for reasons that are thought unrelated to the assessment outcome (image out of focus, ambient light ingress) will not be imputed. Otherwise missing data will be considered as a disagreement in the calculation of agreement. Secondary analyses based on imputing all missing data as a disagreement will be conducted, if appropriate.

Otherwise missing data will not be imputed.

## **10.0 Subject Disposition and Pre-Imaging Information**

### **10.1 Subject Disposition**

Study completion and discontinuation details, inclusion/exclusion criteria, population assignment, and protocol deviations will be listed.

The number of subjects attending each study visit, completing the study, withdrawing from the study and the primary reason for withdrawal will be tabulated.

The number and percentage of subjects in each analysis population will be tabulated. In the case of the agreement population, this includes the number of subjects with a tooth with no visible lesion, with a tooth with an active lesion or with either.

The number and percentage of subjects with deviations and reason for deviation will be tabulated.

### **10.2 Demographic Characteristics**

Demographic parameters will include date of birth, age, gender and ethnicity. Demographics will be listed and tabulated using descriptive statistics.

$$\text{Age} = ((\text{Date of informed consent}) - (\text{Date of Birth}) + 1) / 365.25$$

### **10.3 Relevant Medical History**

Details of relevant medical history and medications (known sensitivities or allergies to photoproteins, and use of calcium supplements and antacids) will be listed.

### **10.4 Oral Hygiene**

Details of oral hygiene will be listed and the number and percentage of subjects within each oral hygiene category (frequency that teeth are brushed, use of mouthwash, frequency of mouthwash use and whether any other products are used) will be tabulated.

### **10.5 Calcivis System**

Details of Calcivis System preparation and imaging set-up will be listed. Details of the independent review will also be listed.

The post-imaging checklist from each study visit will also be listed.

## **11.0 Agreement**

The ICDAS defined tooth status (no visible lesions/active lesions) by the original Dentist, and the independent dentist assessment using the Calcivis System (no luminescence/luminescence) will be listed for each tooth.

A table will be presented cross-tabulating the original dentist ICDAS defined tooth status with the independent reviewer Calcivis finding.

Agreement between the ICDAS defined tooth status and Calcivis finding will be summarised using the negative and positive percent agreement as follows:

- The percentage of teeth with no visible lesion that are assessed as showing no luminescence by the Calcivis System (negative percent agreement);
- The percentage of teeth with an 'active lesion' that are assessed as showing

luminescence by the Calcivis System (positive percent agreement).

The hypothesis that agreement is greater than 0.5 will be tested using an exact binomial test and an exact one-sided 97.5% Clopper-Pearson confidence interval will be presented.

Secondary analyses based on imputing all missing data as a disagreement will be conducted, if appropriate.

## **12.0 Patient and User Questionnaires**

Details of Patient and User Questionnaires will be listed and responses to each question will be summarised using frequency counts and percentages.

## **13.0 Safety**

Safety will be assessed from records of Adverse Events.

### **13.1 Adverse Events**

AEs will be collected from the point of informed consent.

A procedure emergent AE (PEAE) is defined as an AE with start date on or after the start of the Calcavis system procedure. AEs with unknown start date will be assumed to be procedure emergent unless the end date is known to be before the procedure commenced.

All adverse events and serious adverse events will be listed. PEAEs will be flagged in the listings.

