4. STUDY OBJECTIVES AND ENDPOINTS

4.1 Primary Objectives

Performance of the Calcivis System, as measured by the presence or absence of elevated luminescence on the surface of the tooth determined from intra-oral image mapping of that surfaces of teeth (with or without a visible lesion).

Primary Safety Objective

Safety of the Calcivis System, as measured by the collection of all adverse events

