In May 2014, the first formal Post-Approval Clinical Study was performed in adults (16 to 25 yrs old) using the advanced prototype Calcivis System. The Primary Objectives of the study were to assess the Performance and Safety of the Calcivis System, and the Secondary Objective was to assess user experience with the Calcivis System (both User and Patient). A total of 42 patients were recruited to the study from three UK, General Dental Practices, to obtain a total of 31 evaluable patients. Eligible patients were those with interpretable images of both a tooth with no visible lesion identified (ICDAS Code 0) and a tooth with a suspected visible lesion identified (ICDAS Code 1, 2 or 3). Images from 11 patients were not eligible for interpretation due to confounding factors including ambient light ingress, gross saliva contamination and poor disclosing solution coverage on the tooth surface. All these issues have been addressed in the design phase for the new commercial Calcivis System which is the subject of this study.

All 42 patients were included in the Safety Population – two adverse events were recorded – bleeding gums and slight gum abrasion – both were device-related, non-serious and asymptomatic to the patients with no action required. One other adverse event was recorded as a device deficiency when the device jammed and did not dispense fluid.

31 patients were included in the Agreement Population – analysis of the level of agreement between the ICDAS scores and elevated luminescence, (Y/N) as defined by the Investigators.

For the primary study objectives, the study results concluded that: -

1. The Calcivis System was safe in clinical use as determined by the low number and minor nature of the adverse events recorded.

2. Analysis of the overall level of agreement between elevated luminescence and the presence of lesions predicated as active by the Investigators showed agreement in 47 of the 65 teeth imaged (72.3 %) which was statistically significant, not due to chance and above the expected level of 70%.

(Of the 31 teeth identified by the Investigators with no visible lesions, 26 showed no elevated luminescence using the Calcivis System – corresponding to a negative percentage agreement of 83.9%. Of the 34 teeth with visible lesions identified by the Investigators, 21 showed elevated luminescence using the Calcivis System – corresponding to a positive percentage agreement of 61.8%).

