9.2 Collection and Reporting of Adverse Events

It is the responsibility of the Investigator at the site to ensure that all adverse events (AEs, SAEs, ADEs, SADEs (ASADEs and USADEs) and device deficiencies) occurring during the course of the study are recorded on the Adverse Event Form. Details recorded should include the following information:

- A description of the event
- The dates of the onset and resolution
- Any action taken
- The outcome
- The relationship to the device
- Whether or not the adverse event is serious
- Whether the adverse events arises from insufficiencies in the IFU
- Whether the adverse event arises from user error

Any adverse events that occur during the course of the study should be treated by established standards of care that will protect the life and health of the study patients.

Adverse events can be observed directly by the site Investigator or staff, or can be spontaneously reported by the patient. In addition each patient should be questioned about adverse events at each study visit. In all cases it is the responsibility of the site Investigator to collect the information and record as outlined above. All adverse events should be followed up for the duration of the study.

In the case of SAEs, SADEs (ASADEs and USADEs) – including those resulting from device deficiencies), these must be reported to the study Sponsor and to the relevant Ethics Committee according to the term of approval and in addition, any local adverse event reporting guidelines should be followed.

Anticipated Adverse Events are as follows:

- Infection due to cross-contamination from other patient
- Irritation / erythema due to reaction to Disclosing Solution
- Hypersensitivity to the Disclosing Solution

- Pain or discomfort due to presence of intra-oral imaging device in mouth
- Damage/ trauma to soft tissue due to presence of intra-oral imaging device in mouth
- Choking hazard from patient biting down on Applicator

Serious Adverse Events, Serious Adverse Device Effects and Unanticipated Adverse Device Effects must be reported to the Sponsor, within 24 hours of becoming aware of the event. In addition a written report is to be provided by the Investigator within 5 working days.

SAEs, SADEs and UDAEs should be sent by email within the specified timelines to:

[contact] and [contact]

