10.2 Statistical Analysis

General Considerations

The planned statistical analysis will be fully described in a Statistical Analysis Plan, which will be finalised prior to the locking of the study database. The main details of the planned analysis are described below.

The statistical analysis will be performed using SAS version 9.2 or higher.

All statistical tests will be conducted one-sided with a 2.5% level of significance and no adjustment will be made for multiple testing.

Analysis Populations

All patients on whom the Calcivis System is used will be included in the Safety Population.

The Agreement Population will include all teeth on which there is a dentist ICDAS score.

Analysis

The percentage agreement of the original dentist ICDAS score and the independent reviewer Calcivis finding ('no luminescence' or 'luminescence') will be presented along with an exact one-sided 97.5% confidence interval and p-value comparing the percentage agreement to 0.5 for the following:

- Teeth rated with 'no visible lesion' that are assessed as 'no luminescence' by the Calcivis System;
- Teeth rated with an 'active lesion' that are assessed as 'luminescence' by the Calcivis System.

The analysis of agreement will be performed on the Agreement Population.

The agreement between the original dentist ICDAS score and Calcivis finding will be analysed in the same manner.

User and patient questionnaire data and adverse events will be summarised descriptively for the Safety Population.

Missing Data

Missing data arising from teeth where the Calcivis System assessment is uninterpretable for reasons that are thought unrelated to the assessment outcome, will not be imputed. The reasons will be pre-defined in the Statistical Analysis Plan. Otherwise missing data will be considered as a disagreement in the calculation of agreement. Secondary analyses based on imputing all missing data as a disagreement will be conducted, if appropriate.

Otherwise missing data will not be imputed.

Interim Analysis

No interim analysis is planned for this study.

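### Do the adverse event summary and the second agreement analysis in Protocol 10.2 require additions to the SAP?

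*SAP*

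**What the plan says.** **Adverse events.** Protocol 4.1 defines the primary safety objective as "Safety of the Calcivis System, as measured by the collection of all adverse events". Protocol 10.2 says: "User and patient questionnaire data and adverse events will be summarised descriptively for the Safety Population". SAP 13.0 states that "Safety will be assessed from records of Adverse Events", and SAP 13.1 gives the output: "All adverse events and serious adverse events will be listed. PEAEs will be flagged in the listings". SAP 13.1 also defines procedure-emergent events and how to classify an event whose start date is unknown. The outputs are Listings 14 and 15. For the questionnaires, SAP 12.0 says: "Details of Patient and User Questionnaires will be listed and responses to each question will be summarised using frequency counts and percentages", and Tables 8 and 9 follow.

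**Device deficiencies.** Protocol 9.2 puts these on the same form as adverse events: "and device deficiencies) occurring during the course of the study are recorded on the Adverse Event Form".

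**Agreement.** After setting out the analysis against the independent reviewer's reading, Protocol 10.2 adds: "The agreement between the original dentist ICDAS score and Calcivis finding will be analysed in the same manner". No reader is named in that sentence. SAP 11.0, Tables 5 to 7 and Listing 11 use the independent reading only.

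**The concern.** The protocol makes one promise about two kinds of data, and the SAP appears to keep half of it. Questionnaires, which serve the secondary objective, get counts and percentages; adverse events, which serve a primary objective, get listings. With no table specified, someone must decide after seeing the data whether to count patients or events, which relationship categories count as device-related, and whether device deficiencies are included. If that choice could colour the safety conclusion, it should be fixed beforehand.

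The agreement sentence raises a similar worry. If it means the treating investigator's own reading at Visit 1, which the Schedule of Events and Protocol 8.2 provide for, then an analysis in the protocol has no place in the SAP.

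**Working it through.** The plan gives no safety figure to reproduce, so the check compares the texts and then sizes the likely data.

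**1. Outputs (SAP 14.0 and 16.0).** Of 9 tables, 0 summarise adverse events; the only trace is adverse event as a withdrawal reason in Table 1. Tables 8 and 9 (2 of 9) cover questionnaires. Tables 5 to 7 (3 of 9) cover agreement, all on the independent reading; Table 7 is the missing-as-disagreement version, not a second reader.

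**2. What the listings carry.** Listing 14 shows, for each event, the procedure date, device code or lot, onset and stop dates, outcome, severity, action, relationship to procedure and to device, seriousness, whether the instructions were at fault, whether the user was at fault, and the procedure-emergent mark. Listing 15 gives the reason an event was serious and whether it was anticipated. Listing 10 records yes or no for any adverse event by patient and visit. Table 1 supplies the Safety Population denominator. Patient and event counts for procedure-emergent, device-related and serious events can all be made from these.

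**3. Likely number of events.** Protocol 5.7 reports for the previous study that "two adverse events were recorded" among 42 patients, plus one further event classed as a device deficiency. The Synopsis expects 85 to 180 patients. Assuming the same rate:

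- Adverse events: 2/42 = 0.0476 per patient; × 85 = 4.0; × 180 = 8.6.
- With device deficiencies: 3/42 = 0.0714 per patient; × 85 = 6.1; × 180 = 12.9.

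Two events are little to go on. The exact 95% Poisson interval for a count of 2 is 0.24 to 7.22. Scaling by 85/42 gives 0.5 to 14.6 events; scaling by 180/42 gives 1.0 to about 31. The earlier study also used a prototype in patients aged 16 to 25, while this one uses a newer device from age 6. Even about 31 events can be read and counted from a listing.

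**4. Device deficiencies.** Protocol 9.1 counts malfunctions, use errors and poor labelling as deficiencies. Listing 14 has device, user-error and instructions columns, so a deficiency recorded on the Adverse Event Form could appear there, though without its own label. The header of Listing 14 is scrambled in the available text, so a missing column cannot be inferred. Protocol 10.2 promises no separate deficiency summary.

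**5. The agreement sentence.** There are two readings. (a) It restates the analysis just described: SAP 11.0 itself shortens the independent reviewer's reading to the same phrase, the Calcivis finding. (b) It means the investigator's Visit 1 reading; otherwise it repeats its neighbour. The documents do not settle which. Under (a) nothing is missing. Under (b) the method is already fixed as the same one, the shells of Tables 5 and 6 can be rerun, and the result is secondary because Protocol 8.5 assigns the primary analysis to the independent reading.

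**6. Effect on the main result.** None. The success rule uses only the two agreement tests. The planned 81 teeth per population reproduces: at least 50 agreements are required, exact one-sided alpha is 0.0224, and power at 70% agreement is 0.957. Jointly this is 0.957 × 0.957 = 0.916 if the two populations are independent. No safety output enters that calculation.

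**The case for a change.** The best case for a change is that a listing is not a summary, and the SAP's own usage shows it: demographics are to be both listed and tabulated, and questionnaires both listed and summarised. SAP 9.1 sets formats for summary statistics but commits to no adverse event summary. The previous study's safety conclusion rested partly on the low number of events, and that number was 2 or 3 depending on whether the device deficiency counted. Fixing the counting rule would take one table from data already collected.

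Much of this stands. The two documents differ, no SAP sentence removes the difference, and the table would be cheap. What does not stand is that the safety result is left open. The objective carries no rate, threshold or hypothesis, there is no comparison arm, and all events are to be shown with the attributes that any count would use. A reader who prefers another cut, such as treating only probable or definite events as device-related, can make it from Listing 14. Selective counting has little room when the complete record is disclosed.

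On agreement, reading (b) is reasonable and would match the previous study, where investigators judged luminescence. But an omission is not shown when it is unclear that anything was owed. Whether the investigator's reading is captured per tooth also depends on the case report form, which is not among the documents.

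**Conclusion.** No change to the plan follows. The adverse event point is a minor reporting inconsistency: the protocol commits to a descriptive summary, and the SAP supplies the full data without the table shell. Analysts working under that commitment would add the counts as a matter of course, and the listings let anyone verify them. At the earlier rate the table would condense about 4 to 9 events, or 6 to 13 with device deficiencies. The agreement sentence is an ambiguity worth asking the sponsor about, not a demonstrated gap.

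This rests on three assumptions: event numbers stay small enough to read from a listing, even at the upper figure of about 31; the listings are produced in full as specified; and the supplied protocol matches the one behind the SAP. The last cannot be confirmed, since SAP 1.0 cites version 4 of the Clinical Study Plan and the supplied text does not show its own version.

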## 14.0 Table Mock Ups

Table 1	Patient Disposition	Safety Population
Table 2	Protocol Deviations	Safety Population
Table 3	Demography	Safety Population
Table 4	Oral Hygiene	Safety Population
Table 5	Original Dentist Assessment of ICDAS Score and Independent Dentist Interpretation of Calcivis System Assessment	Agreement Population
Table 6	Agreement between Original Dentist ICDAS Assessment and Independent Dentist Interpretation of Calcivis System Assessment	Agreement Population
Table 7	Agreement between Original Dentist ICDAS Assessment and Independent Dentist Interpretation of Calcivis System Assessment – Secondary Analysis (if required)	Agreement Population
Table 8	Patient Questionnaires	Safety Population
Table 9	User Questionnaires	Safety Population

## 15.0 Figure Mock Ups

No Figures are required for this study.

## 16.0 Data Listing Mock Ups

Each listing will include all patients that provide any data relevant to the listing. Listings will be ordered by patient number.

Listing 1	Patient Disposition	Safety Population
Listing 2	Inclusion and Exclusion Criteria	Safety Population
Listing 3	Population Assignment	Safety Population
Listing 4	Protocol Deviations	Safety Population
Listing 5	Demography	Safety Population
Listing 6	Relevant Medical History and Medications	Safety Population
Listing 7	Oral Hygiene	Safety Population
Listing 8	Calcivis System Preparation	Safety Population
Listing 9	Calcivis System Imaging	Safety Population
Listing 10	Post-Imaging Checklist	Safety Population
Listing 11	Independent Imaging Interpretation and Analysis	Safety Population
Listing 12	Patient Questionnaires	Safety Population
Listing 13	User Questionnaires	Safety Population
Listing 14	Adverse Events	Safety Population
Listing 15	Serious Adverse Events	Safety Population

Table 1 Patient  
Disposition Safety

Population

	Overall (N=XX)
Attended Visit 1	X ( xx.x %)
Attended Visit 2	X ( xx.x %)
Completed Study	X ( xx.x %)
Withdrew from Study	X ( xx.x %)
Reason for Withdrawal	
Consent withdrawn by patient	X ( xx.x %)
Investigator withdrew patient	X ( xx.x %)
Lost to follow-up	X ( xx.x %)
Adverse Event	X ( xx.x %)
Death	X ( xx.x %)
Other	X ( xx.x %)
Population	
Safety	X ( xx.x %)
Agreement 	X ( xx.x %)
Tooth with no visible lesion	X ( xx.x %)
Tooth with active lesion	X ( xx.x %)

Produced : xxxxxxxx xx:xx (Page xx of yy)

 Subjects with a tooth with no visible lesion or a tooth with an active lesion or both. Table supported by Listings 1 & 3

Table 2 Protocol

Deviations Safety  
Population

	Overall (N=XX)
Any Protocol Deviations	X ( xx.x %)
Informed Consent Process	X ( xx.x %)
Inclusion/Exclusion	X ( xx.x %)
Study Procedure	X ( xx.x %)
Other	X ( xx.x %)

Produced : xxxxxxxx xx:xx (Page xx of yy)

Table supported by Listing 4

Table 3 Demography  
Safety Population

		Overall (N=XX)
Age (years)	n	X
	Mean	XX.X
	SD	XX.XX
	Minimum	XX
	Median	XX.X
	Maximum	XX
Gender	Male	X ( xx.x %)
	Female	X ( xx.x %)
Ethnic Group	Hispanic or Latino	X ( xx.x %)
	Asian	X ( xx.x %)
	Black	X ( xx.x %)
	White	X ( xx.x %)
	Other	X ( xx.x %)

Produced : xxxxxxxxx xx:xx (Page xx of yy)

Table supported by Listing 5

Table 4

Oral Hygiene

Overall (N=XX)		
Teeth Brushed	Once per day	X ( xx.x %)
	Twice per day	X ( xx.x %)
	Three times per day	X ( xx.x %)
	Other	X ( xx.x %)
Use Mouthwash	Yes	X ( xx.x %)
	No	X ( xx.x %)
Mouthwash Used	Once per day	X ( xx.x %)
	Twice per day	X ( xx.x %)
	Three times per day	X ( xx.x %)
	Other	X ( xx.x %)
Other Products	Yes	X ( xx.x %)
	No	X ( xx.x %)

Produced : xxxxxxxxx xx:xx (Page xx of yy)

Table supported by Listing 7

  
 Table 5  
 Original Dentist Assessment of ICDAS Score and Independent Dentist Interpretation of Calcivis System Assessment  
 Agreement Population

As Assessed by Original Dentist using ICDAS	As Interpreted by Calcivis System			
	No Luminescence	Luminescence	Missing	Total
ICDAS 0	X ( xx.x %)	X ( xx.x %)	X ( xx.x %)	X ( xx.x %)
ICDAS 2	X ( xx.x %)	X ( xx.x %)	X ( xx.x %)	X ( xx.x %)
ICDAS 3	X ( xx.x %)	X ( xx.x %)	X ( xx.x %)	X ( xx.x %)
Total	X ( xx.x %)	X ( xx.x %)	X ( xx.x %)	X ( xx.x %)

Produced : xxxxxxxxxxxx xx:xx (Page xx of yy)

Table supported by Listings 9 & 11

Percentages are calculated from total number of teeth assessed by Calcivis system

Table 6  
Agreement between Original Dentist ICDAS Assessment and  
Assessment  
Agreement Population

Independent Dentist Interpretation of Calcivis System

Original Dentist ICDAS Assessment	N	Agreement		
		n (%)	P-value	1 – sided 97.5% CI
No visible lesion	X	xx (xx.x%)	x.xxx	x.xx
Active lesion	X	xx (xx.x%)	x.xxx	x.xx
All teeth	X	xx (xx.x%)		

Produced : xxxxxxxx xx:xx (Page xx of yy)

N = Number of teeth with no visible lesion or active lesion respectively; n (%) = Number (%) of teeth with no luminescence or luminescence out of the number of teeth with no visible lesion or active lesion respectively.

Table supported by Listings 9 & 11

*Programmers note: Repeat table for*

*Table 7 Agreement between Original Dentist ICDAS Assessment and Independent Dentist interpretation of Calcivis System Assessment - Secondary Analysis -Agreement Population*

Table 8

Safety Population

Patient Questionnaires

Question	Response	Overall (N=XX)
How would you rate your overall experience with the Calcivis System? 	Good	X ( xx.x %)
	Neither good nor bad	X ( xx.x %)
	Bad	X ( xx.x %)
Did you find seeing the images of your teeth and having the dentist explain your situation helpful? 	Helpful	X ( xx.x %)
	Neither helpful nor unhelpful	X ( xx.x %)
	Unhelpful	X ( xx.x %)

---

Produced : xxxxxxxxx xx:xx (Page xx of yy)

 6-11 year olds were asked "How do you feel about your dentist using the Calcivis system?"

 6-11 year olds were asked "Did you find seeing the pictures of your teeth and having the dentist explain them to you helpful?"

Table supported by Listing 12

Table 9  
Safety Population

User Questionnaires

Question	Response	Overall (N=XX)
How easy was it to prepare the Calcivis System?	Easy	X ( xx.x %)
	Neither easy nor difficult	X ( xx.x %)
	Difficult	X ( xx.x %)
How easy was it to use the device?	Easy	X ( xx.x %)
	Neither easy nor difficult	X ( xx.x %)
	Difficult	X ( xx.x %)
How would you rate your overall experience with the Calcivis System?	Good	X ( xx.x %)
	Neither good nor bad	X ( xx.x %)
	Bad	X ( xx.x %)
Were the instructions provided sufficient for you to understand how to use the Calcivis System?	Easy	X ( xx.x %)
	Neither easy nor difficult	X ( xx.x %)
	Difficult	X ( xx.x %)

Produced : xxxxxxxx xx:xx (Page xx of yy)

Table supported by Listing 13

Listing 1

Patient

Disposition

Safety

Population

---

Site  
nt

Patie

Informed Consent

Did the

Patient

Date of Completion/

Number	Number	Date	Time	Complete the Study	Withdrawal	Reason for Withdrawal
XX	YY	DDMMYYYY	hh:mm	Yes	DDMMYYYY	
	YY	DDMMYYYY	hh:mm	No	DDMMYYYY	Consent withdrawn by patient
	YY	DDMMYYYY	hh:mm	No	DDMMYYYY	Investigator withdrew patient
	YY	DDMMYYYY	hh:mm	No	DDMMYYYY	Lost to follow-up
	YY	DDMMYYYY	hh:mm	No	DDMMYYYY	Adverse event
	YY	DDMMYYYY	hh:mm	No	DDMMYYYY	Death
	YY	DDMMYYYY	hh:mm	No	DDMMYYYY	Other: XXXXXXXXXX

---

Produced : xxxxxxxxx xx:xx (Page xx of yy)

## Listing 2

Inclusion and Exclusion Criteria  
Safety Population

Site Number	Patient Number	Criterion Type	Criterion Number	Criterion Text	Criterion Response
XX	YY	Inclusion	1	Patient must be $\geq 6$ years old	Yes
			2	Patient must have one unrestored, accessible, free smooth buccal surface on a canine or incisor, away from the gingival surface identified with no visible lesion (coded ICDAS 0) and/or	Yes
			3	Patient must have one unrestored, accessible, erupting or erupted molar or pre-molar with a visible lesion identified (coded ICDAS 2 or 3) in a plaque stagnation area	No
			4	Patient and/or parent or guardian must be willing and able to give written informed consent	Yes
			5	Patient and/or parent or guardian must be willing and able to adhere to study schedule	Yes
		Exclusion	1	Any patient with recent tooth bleaching (within previous two weeks of treatment with the Calcivis System)	No
			2	Any patient having on-going re-mineralisation treatment including, but not limited to high concentration prescription fluoride toothpaste	No
			3	Any patient with a fixed orthodontic appliance	Yes
			4	Any patient currently taking part in a clinical research study, or has taken part in a clinical research study in the previous three months	No
			5	Pregnant and/or nursing mothers	No

Listing 3  
Safety Population

Population Assignment

Site Number	Patient Number	Population		
		Safety	Agreement	Lesion
XX	YY	Yes	Yes	No visible lesion
	YY	Yes	No	Active lesion

---

Produced : xxxxxxxxx xx:xx (Page xx of yy)

Listing 4  
Safety Population

Protocol Deviations

Site Number	Patient Number	Date of Protocol Deviation	Details of Protocol Deviation	Reason for Protocol Deviation	Date Reported to Calcivis	Action Taken
XX	YY	DDMMYY	XXXXXXXXXX	Informed Consent Process	DDMMYY	XXXXXXXXXX
	YY	DDMMYY	XXXXXXXXXX	Inclusion/Exclusion	DDMMYY	XXXXXXXXXX
	YY	DDMMYY	XXXXXXXXXX	Study Procedure	DDMMYY	XXXXXXXXXX
	YY	DDMMYY	XXXXXXXXXX	Other: XXXXXX	DDMMYY	XXXXXXXXXX

---

Produced : XXXXXXXX xx:xx (Page xx of yy)

Listing 5  
Demography  
Safety Population

Site Number	Patient Number	Date of Birth	Age 	Gender	Race
XX	YY	DDMMYYYY	xx	Male	Hispanic or Latino
	YY	DDMMYYYY	xx	Female	Asian
	YY	DDMMYYYY	xx		Black
	YY	DDMMYYYY	xx		White
	YY	DDMMYYYY	xx		Other: XXXXXXXX

---

Age = (Date of informed consent–Date of Birth+1)/365.25.

Produced : xxxxxxxx xx:xx (Page xx of yy)

Listing 6  
Safety Population

Relevant Medical History and Medications

Site Number	Patient Number	Question	Response	Name	Frequency	Date of Last Dose	Time of Last Dose
XX	YY	Any known sensitivities or allergies to photoproteins?	No				
		Do you take any calcium supplements?	Yes	XXXXXXXX XXXXXX	DDMMYYYY	HH:MM	
		Do you take any antacid tablets?	Yes	XXXXXXXX XXXXXX	DDMMYYYY	HH:MM	

---

Produced : xxxxxxxxx xx:xx (Page xx of yy)

Listing 7 Oral

Hygiene  
Safety Population

Site Number	Patient Number	Question	Response	Details
XX	YY	Which toothpaste do you use most often?	XXXXXXXXXX	
		How many times per day do you brush your teeth?	Once per day Twice per day Three times per day Other	XXXXXXXXXX XXXXXXXXXX
		Do you use mouthwash?	Yes No	XXXXXXXXXX XXXXXXXXXX
		On average, how many times per day do you use mouthwash?	Once per day Twice per day Three times per day Other	XXXXXXXXXX XXXXXXXXXX
		Do you use any other dental products?	Yes No	XXXXXXXXXX XXXXXXXXXX

---

Produced : XXXXXXXXX xx:xx (Page xx of yy)

Site	Patient			Time
Procedures				
Number	Number	Visit	Question	Response
		Started		
XX	YY	Visit 1	Has the Calcavis System been set up according to the manufacturers Instructions for Use?	Yes
		HH:MM		No
			Were teeth cleaned according to teeth cleaning protocol?	Yes
				No
			Was patient rinsed out thoroughly with tap water?	Yes
				No
			Have colour photographs been taken of each selected tooth surface?	Yes
				No

---

Produced : xxxxxxxxx xx:xx (Page xx of yy)

Listing 9  
Safety Population

Calcivis System Imaging

Site Number	Patient Number	Visit Visit 1	Visit Date DDMMYYYY	Tooth	Tooth ID	Surface to be Imaged	ICDAS code	Inactive or Active	Number of Images	Image to be used
XX	YY			1	xx	Buccal	0	Inactive	1	1
				2	xx	Occlusal	2 or 3	Active	2: XXXXXX	1

---

Produced : Produced : xxxxxxxxx xx:xx (Page xx of yy)

Listing 10  
Safety Population

Post-Imaging Checklist

Site Number	Patient Number	Visit	Visit Date	Were images reviewed with the patient?	Did any Adverse Events occur?	Has the patient been given a Patient Questionnaire / Visual Analogue Scale to complete?	Is the visit 7-14 days after visit 1?	Has final oral exam been carried out?
XX	YY	Visit 1	DDMMYYYY	Yes	Yes	Yes		
				Yes	Yes	No		
				Yes	No	Yes		
				No	Yes	Yes		
				Yes	No	No		
				No	Yes	No		
				No	No	Yes		
				No	No	No		
		Visit 2			Yes		Yes	Yes
					Yes		Yes	No
					Yes		No	Yes
					No		Yes	Yes
					Yes		No	No
					No		Yes	No
					No		No	Yes
					No		No	No

Produced : Produced : xxxxxxxx xx:xx (Page xx of yy)

Listing 11  
Independent Imaging Interpretation and Analysis

Safety Population

Site Calcivis Number	Patient Number	Original Dentist Visit	Date	Original Dentist Tooth ID	ICDAS Rating	ICDAS Activity	Luminescence Detected from System - Independent Dentist
XX	YY	Visit 1	DDMMYYYY	Xx xx	Xx xx	No visible lesion - inactive Active lesion	Yes No

Produced : xxxxxxxx xx:xx (Page xx of yy)

Site Number	Patient Number	Question Number	Question Text	Response	Comments
XX	YY	Visit 1	1	How would you rate your overall experience with the Calcivis System?	Good Neither good nor bad Bad
			2	Did you find seeing the images of your teeth and having the dentist explain your situation helpful?	Helpful Neither helpful nor unhelpful Unhelpful

---

Produced : xxxxxxxxx xx:xx (Page xx of yy)

Programming note: Questions may differ based on the age of the patient. Please output the relevant question for the patient age.

Listing 13  
User Questionnaires

Safety Population

Site Number	Investigator	Dental Nurse	Number of Procedures	Date Completed	Question Number	Question Text	Response	Comments
XX	xxxxxxxx	xxxxxxxx	xx	DDMMYYYY	1	How easy was it to prepare the Calcivis System?	Easy Neither easy nor difficult Difficult	XXXXXXXXXX
					2	How easy was it to use the device?	Easy Neither easy nor difficult Difficult	XXXXXXXXXX
					3	How would you rate your overall experience with the Calcivis System?	Good Neither good nor bad Bad	XXXXXXXXXX
					4	Were the instructions provided sufficient for you to understand how to use the Calcivis system?	Easy Neither easy nor difficult Difficult	XXXXXXXXXX

Produced : xxxxxxxx xx:xx (Page xx of yy)

Inv Name/ Site Number	Patient Number	Verbatim No.	Date of Procedure	Device(s) - Code/ Lot Number			Onset Number	Date/ Stop Date	Status/ Outcome	Severity	Action Taken	Relationship to Procedure	Device	Did AE arise from insufficiencies in the Instructions for use?	Did the AE arise due from user error?
SAE?															
XXXXX/ YY	1*	xxxxxxxxxx	DDMMYY	xxxxx	DDMMYY	/	Continued/	Mild	None	Unrelated	Unrelated	Yes		Yes	
Yes							DDMMYY	ongoing	Moderate	Medical	Possible	Possible	No	No	
XX							DMMYY	Recovered	Severe	Therapies	Probable	Probable			
No							Ongoing	Recovered		Procedural	Definite	Definite			
								with		Other:					
								sequelae		XXXXXX					
								Death							

Produced : xxxxxxxx xx:xx (Page xx of yy)\* Procedure emergent adverse event.

Inv

Name/

Site	Inv Patient	Verbatim	Onset Date/	Date Became	Date Reported	Reason for	Is the AE
Number	Number	No.	Term Anticipated?	Stop Date	Serious	to Sponsor	Serious
XXXXXXX/ YY	1*	xxxxxxxxxx	DDMMYY/	DDMMYY	DDMMYY	Death	Yes
XX			DDMMYY			Life-threatening illness or injury	No
			DMMYY/			Resulted in a permanent impairment of a body structure or a body function	
			Ongoing			In-patient hospitalization required	
						In-patient hospitalization prolonged	
						Resulted in a medical or surgical intervention to prevent a permanent impairment of a body structure or a body function	
						Foetal distress, foetal death or congenital anomaly or birth defect	

Produced : xxxxxxxxx xx:xx (Page xx of yy)

\* Procedure emergent adverse event.
